We will have excellent power to detect clinically relevant changes in RV strain ($\alpha = 0.05$) (Table 7). A $\geq 5\%$ improvement in RV strain (measured by echocardiography; less precise than MRI) occurs with approved PAH therapies and predicts clinical stabilization and survival in PAH.⁵⁶ We have more than enough power to detect this estimate, and effects even as small as 3%. We need this number of patients in order to perform sex-specific analyses (and test for treatment x sex interaction), where we will have 80% power to detect a 4% difference in sex-specific analyses with the presence of an interaction. Power for treatment x PAH subtype interactions will mirror these estimates. We will also have sufficient power to detect changes which approach clinical relevance in RVEF^{61, 139} and NT-proBNP¹⁴⁰ ($\alpha = 0.05$) (Table 8).

C8.p2. Aim 2: Power to detect differences in nitrate and ET-1 levels.

We will have excellent power to detect small ($0.05 \mu\text{M}$) differences in nitrite levels with DHEA treatment based on conservative previously observed estimates ($\alpha = 0.05$).^{25, 141} We will have excellent power to detect small (well-less than 2 pg/mL) differences in ET-1 levels with DHEA treatment ($\alpha = 0.05$). Changes of this magnitude would be consistent with clinically relevant changes in ET-1 with ERAs.¹⁴²

C9. Aim 3: PAEC response to DHEA. In order to minimize burden of the trial participants (and to guarantee more catheter tips), PAECs from men and women undergoing right heart catheterization at the RIHPHC as part of PAH diagnosis or treatment and meeting the same inclusion/exclusion criteria for the cross over trial will be included. As with our preliminary data, these experiments will be performed in our Centers of Biomedical Research Excellence in Stem Cell Biology (PI: [name], P20 GM103468) and Cardiopulmonary Vascular Biology (PI: [name]; Laboratory Core PI: [name], P20 GM103652). We will also examine the effect of DHEA on PAECs obtained from two additional sources: 1) commercially available human PAECs, 2) those obtained from the distal pulmonary circulation of PAH lung explants available through the Pulmonary Hypertension Breakthrough Initiative (PHBI) (PI [name], R24 HL123767; see letter of support).

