performed in our laboratory¹⁴⁵ with concurrent confirmation of PAEC phenotype. We will also determine the effect of DHEA in commercially available disease free PAECs. These conditions will then be used in experiments to assess DHEA's effects on NO and ET-1 synthesis in PAECs from both sexes with PAH. All experiments will be repeated with 1) exposure to E2 for comparison and 2) in PAECs from lung explants to determine if distal and proximal PAECs respond in a similar way to DHEA.

C9.a. Analysis Plan Aim 3: PAEC response to DHEA. Wilcoxon signed-rank tests and analysis of variance will be used to compare ET-1 and eNOS expression and nitrite and nitrate levels before and after DHEA treatment and across cells from men and women.

C10. Study timeline. Based on prior recruitment rates and fractions, we will be able to enroll 4-7 subjects per year as outlined in the study timeline. A five year mechanism is proposed and is needed in order to ensure adequate inclusion of men and completion of the protocol for subjects recruited later in the study period to allow adequate time for follow-up, biomarker and data analysis (which cannot be completed until all subjects enrolled later in the study complete the 42 week crossover trial protocol).

Table 9. Study timeline

	Yr 1	Yr 2	Yr 3	Yr 4	Yr 5
Start-up: Drug purity testing	Mos 1-6				
Relational trial database buildout	Mos 1-6				
Policies and Procedures, IRB approval	Mos 1-6				
Aim 1,2: Cross-over enrollment	n = 4	n = 7	n = 7	n = 6	n = 2
Aim 3: Commercial cells, PHBI	X	X	X	X	
Aim 3: PAECs, patient catheterizations	n = 15	n = 15	n = 15	n = 15	n = 15
Lab/results analysis				X	X
Manuscript/grant preparation				X	X

C11. Expected results

C11.a. Aims 1 and 2. Active treatment with DHEA will be associated with an improvement in RV strain pattern, lower ET-1 levels and higher nitrite and nitrate levels. Markers of maladaptive RV hypertrophy including oxidative stress will also be reduced. Sex

will modify these relationships, with women demonstrating a more robust response to DHEA.

C11.b. Aim 3. NO and cGMP synthesis will be higher and ET-1 secretion will be lower in PAECs from women with PAH than PAECs from men, respectively. Treatment with DHEA will increase eNOS expression and nitrite/nitrate levels and decrease ET-1 secretion. Female cells will demonstrate a more robust and distinct response to DHEA than male cells and E2 exposure respectively.

C12. Potential problems and alternative approaches

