constitute a “missed opportunity” to study results of *in vivo* controlled DHEA exposure *in vitro*. We did not incorporate catheterization into the study protocol in an effort to minimize burden but did restrict eligibility for this aim to match inclusion/exclusion criteria for the trial. We perform dedicated right heart catheterizations in 40 – 60 patients yearly, providing ample opportunities to obtain PAECs from PAH patients. Over the last twelve months since this protocol was initiated, PAEC samples have been collected in 57 patients. The PAECs collected (and their response to DHEA exposure) may not represent the phenotype of PAECs from small resistance vessels in PAH (which will also be included for comparison, Section C9). PAH patients have changes in proximal PAs which contribute to circuit compliance and ventricular coupling¹⁴⁷, however, making the proposed experiments relevant. Moreover, recent studies using induced pluripotent stem cells from dermal fibroblasts of PAH patients showed that derived endothelial cells function the same as distal PAECs isolated from explanted lungs.¹⁴⁸ PAECs obtained from lung explants represent end-stage PAH, whereas our method captures PAECs from patients at variable stages of disease. Finally, this is a very novel approach with which we have become increasingly facile in a disease state in which tissue availability is extremely limited.

C13. Summary. This pilot double-blind cross-over trial will test the efficacy and safety of DHEA in men and women with PAH and will characterize the interaction of sex- and sex-hormones with major pathologic drivers of pulmonary vascular and RV dysfunction. Complementary *in vitro* experiments will offer additional insights into mechanisms of sexual dimorphism in PAH. The first study of its kind, we will build a foundation for sex- and hormone-based treatment precision in this rare and progressive disease.

Amendments and Addendums:

Amendment 1 – PAEC Biobanking and RNA Sequencing

Pulmonary arterial cells (PAECs) collected from catheter tips may undergo RNA sequencing as part of an advanced characterization protocol, representing a continuation of the aims of Aim 3 above. The PAECs for RNA Sequencing will be sourced from the current study’s subjects and from a previous biobank (PI: [name], IRB Committee #: 016311). Furthermore, all PAEC cultures will be preserved for future, unknown testing and stored in accordance with the Lifespan HRPP Specimen banking guidelines.

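### Aim 3's comparison of explant with catheter-tip cells confounds vessel site with disease stage, donor and isolation method, so as planned it cannot show whether distal and proximal cells respond alike (minor)

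*Combined protocol and SAP*

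**What the plan says.** - **Purpose.** C9, item 2 (Cell treatment), repeats all experiments "in PAECs from lung explants to determine if distal and proximal PAECs respond in a similar way to DHEA".
- **Distal source.** C9 names one: "those obtained from the distal pulmonary circulation of PAH lung explants available through the Pulmonary Hypertension Breakthrough Initiative".
- **Proximal patient source.** C9 uses catheter tips, that is, "PAECs from men and women undergoing right heart catheterization at the RIHPHC as part of PAH diagnosis or treatment".
- **Donor eligibility.** For catheter donors, C12.b says the investigators "did restrict eligibility for this aim to match inclusion/exclusion criteria for the trial". No eligibility or matching rule is given for explant donors.
- **Stage.** C12.b states: "PAECs obtained from lung explants represent end-stage PAH, whereas our method captures PAECs from patients at variable stages of disease". It offers this in support of the catheter method and does not connect it to the distal-proximal comparison.
- **Analysis.** C9.a compares the measurements "before and after DHEA treatment and across cells from men and women", using Wilcoxon signed-rank tests and analysis of variance. It names no contrast between cell sources and no term for source, site or stage.
- **Numbers.** Table 9 plans 15 catheter donors in each of five years, which is 5 × 15 = 75. No number of explant donors is given.

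**The concern.** C9 treats explant versus catheter tip as if it were distal versus proximal. By the protocol's own description the two sources also differ in disease stage. They come from different donors, and the catheter-tip culture procedure in C9 applies to only one of them. A difference in DHEA response between the sources could therefore come from site, stage, donor, isolation method or a mixture. A lack of difference could be a site effect offset by another of these.

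This matters because C12.b concedes that catheter-tip cells may not have the phenotype of small resistance vessels, and points to the explant cells as one of its answers. If the comparison cannot isolate site, that answer is weaker than it looks. The stated goal is also to learn whether responses are similar. A test that finds no significant difference would not establish this, and the plan sets no interval or margin by which similarity could be judged.

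**Working it through.** The protocol gives no figure to reproduce: no sample size, effect size, alpha or power is stated for this comparison. The check is to map each cell source to site and stage, then look for anything in the plan that separates the two.

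| Source (C9, C12.b) | Site | Disease stage |
|---|---|---|
| PAH lung explants | distal | end-stage only |
| Catheter tips | proximal | variable, mix not stated |
| Commercial cells | not stated | disease free |

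**Step 1: overlap.** No distal cells from earlier-stage donors are planned. Site could be compared at equal stage only among end-stage cells, which needs catheter donors with advanced disease. Such donors may exist, since C12.b says stage varies and Table 5 sets no upper limit on hemodynamic severity. The plan neither identifies nor matches them.

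**Step 2: other sources.** The disease-free commercial cells cannot separate site from stage within PAH. Proximal cells from the explanted lungs are not mentioned.

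**Step 3: analysis.** C9.a has no term or contrast that would adjust for stage, donor or source.

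**Step 4: what could happen.** All values here are assumed, because the documents give neither the stage mix nor any stage effect. Set the DHEA response of an earlier-stage proximal cell to 1. Let end-stage disease multiply the response by s, let distal site multiply it by d, and let p be the share of catheter donors who are end-stage. Donor and isolation method are taken to have no effect. Then:

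- explant response = d × s
- mean catheter response = 1 − p(1 − s)
- observed ratio = d × s / [1 − p(1 − s)]; the true site ratio is d

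With s = 0.7:

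| p | Mean catheter response | Ratio if d = 1 (no site effect) | Ratio if d = 1.3 |
|---|---|---|---|
| 0 | 1.00 | 0.70 / 1.00 = 0.70 | 0.91 / 1.00 = 0.91 |
| 0.3 | 0.91 | 0.70 / 0.91 = 0.77 | 0.91 / 0.91 = 1.00 |
| 0.5 | 0.85 | 0.70 / 0.85 = 0.82 | 0.91 / 0.85 = 1.07 |
| 1 | 0.70 | 0.70 / 0.70 = 1.00 | 0.91 / 0.70 = 1.30 |

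With no site effect, the sources appear to differ by 30%, 23% or 18% for p = 0, 0.3 or 0.5. With a true site ratio of 1.3, they can look alike. If s = 1, the ratio equals d for every p and stage causes no bias. The row p = 1 shows what restriction to end-stage catheter donors would achieve under these assumptions.

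**The case against.** The strongest reply has four parts.

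1. **The confounding is not total.** A reader might infer from the layout that site and stage can never be separated, or that no catheter donor has end-stage disease. The documents do not support that. Variable stages can include advanced disease, and catheter donors have hemodynamic measurements. This stands: the claim is limited to the plan as written.
2. **Little rests on the comparison.** A reader might infer that it alone decides whether catheter results apply to resistance vessels. C12.b gives two other arguments: proximal arteries are themselves altered in PAH, and stem-cell-derived endothelial cells have been reported to behave like distal explant cells. C8.a frames Aim 3 around NO and ET-1 effects and differences by sex, and C11.b predicts nothing about site. This also stands and is why the point is minor. The stem-cell argument does not concern catheter-tip cells, however, so it does not replace the comparison.
3. **The plan does not say it will read non-significance as similarity.** Correct: C9.a specifies no between-source test, so that misreading is a risk left open and not a planned error. The gap is that C9 sets a question for which C9.a has no analysis.
4. **The stage difference is disclosed, and responses are measured before and after DHEA.** A stage difference in baseline level alone need not bias the comparison of responses. Stage, donor or method must modify the response, and the documents do not show whether any does. This stands as a condition on the bias. It does not rescue the C9 wording, since the documents give no reason to assume that these factors have no effect.

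**Conclusion.** The point holds as a minor one. C9 attributes to the explant comparison a property that the design lacks: as planned, it compares two cell sources, not two vessel sites. Site is confounded with stage, donor and isolation method, partially so on the proximal side. The direction and size of any bias are unknown, and the table above is illustration only. Bias in the comparison requires that at least one of these factors modifies the DHEA response. The before-after comparison within each source and the crossover trial's primary outcome are not affected.

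**What to change.** 1. **Reword C9.** State the purpose as comparing end-stage distal (explant) cells with catheter-derived proximal cells, and draw no conclusion about vessel site alone. Cost: wording.
2. **Add the contrast to C9.a.** Report the between-source difference or ratio in DHEA effect with a confidence interval, and state that a non-significant test will not be read as similarity. Cost: wording and one extra estimate.
3. **Add a sensitivity analysis.** Repeat the comparison restricted to, or adjusted for, catheter-donor severity, with donor sex in the model. Define severity in advance from the hemodynamics of the same catheterization. Functional class is scheduled in Table 6 only for crossover visits, so the analysis should not depend on it. Cost: linking those measurements to the cell samples, and fewer donors and lower precision under restriction. The number of advanced-stage catheter donors and the number of explant donors are not stated, so the loss cannot be estimated now.

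Paired proximal and distal cells from the same explanted lungs would be better, because donor and stage would then be held constant. The documents do not show that the explant source holds such pairs, and C12.b notes that tissue is scarce, so the fix does not depend on them.
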